1. ABBREVIATIONS

AE	Adverse Event
AL	Artemether/lumefantrine
ANC	absolute neutrophil count
ANCOVA	Analysis of Covariance
ATP	According to Protocol
CFR	Code of Federal Regulations
CLIA	Clinical Laboratory Improvement Amendments
CMP	Clinical Monitoring Plan
COC	Certificate of Confidentiality
CONSORT	Consolidated Standards of Reporting Trials
Cr	creatinine
CRF	Case Report Form
DCC	Data Coordinating Center
DHHS	Department of Health and Human Services
DSMB	Data Safety Monitoring Board
DRE	Disease-Related Event
ECG	electrocardiogram
EC	Ethics Committee
eCRF	Electronic Case Report Forms
FDA	Food and Drug Administration
FDAAA	Food and Drug Administration Amendments Act of 2007
FFR	Federal Financial Report
GCP	Good Clinical Practice
GLP	Good Laboratory Practices
GMP	Good Manufacturing Practices
GWAS	Genome-Wide Association Studies
Hgb	Hemoglobin
HIPAA	Health Insurance Portability and Accountability Act
HR	hazard ratio
HSA	human serum albumin
IATA	International Air Transport Association
IB	Investigator's Brochure

ICH	International Conference on Harmonisation
ICMJE	International Committee of Medical Journal Editors
IDE	Investigational Device Exemption
IFA	immunofluorescence assay
IgE	immunoglobulin E
IgG	immunoglobulin G
IND	Investigational New Drug Application
IRB	Institutional Review Board
ISI	inhibition of sporozoite invasion assay
ISM	Independent Safety Monitor
ISO	International Organization for Standardization
ITT	Intention-To-Treat
LSMEANS	Least-squares Means
LMIV	Laboratory of Malaria Immunology and Vaccinology
MedDRA	Medical Dictionary for Regulatory Activities
MOP	Manual of Procedures
MSDS	Material Safety Data Sheet
NASBA	nucleic acid sequence-based amplification
NCT	National Clinical Trial
NIH	National Institutes of Health
NIH IC	NIH Institute or Center
NS	normal saline
OCICB	Office of Cyber Infrastructure and Computational Biology
OHRP	Office for Human Research Protections
PBS	phosphate buffered saline
PCR	polymerase chain reaction
PI	Principal Investigator
QA	Quality Assurance
QC	Quality Control
RNA	ribonucleic acid
SAE	Serious Adverse Event
SAP	Statistical Analysis Plan
SMC	Seasonal Malaria Chemoprophylaxis
SNP	single nucleotide polymorphisms
SOA	Schedule of Activities
SOC	System Organ Class
SOP	Standard Operating Procedure
UP	Unanticipated Problem
US	United States
USTTB	University of Sciences, Techniques and Technology, Bamako

STATEMENT OF COMPLIANCE

The trial will be carried out in accordance with International Conference on Harmonisation Good Clinical Practice (ICH GCP) and the United States (US) Code of Federal Regulations (CFR) applicable to clinical studies (45 CFR Part 46, 21 CFR Part 50, 21 CFR Part 56, 21 CFR Part 312, and/or 21 CFR Part 812).

National Institutes of Health (NIH)-funded investigators and clinical trial site staff who are responsible for the conduct, management, or oversight of NIH-funded clinical trials have completed Human Subjects Protection and ICH GCP Training.

The protocol, informed consent form(s), recruitment materials, and all participant materials will be submitted to the Institutional Review Board (IRB) for review and approval. Approval of both the protocol and the consent form must be obtained before any participant is enrolled. Any amendment to the protocol will require review and approval by the IRB before the changes are implemented to the study. In addition, all changes to the consent form will be IRB-approved; an IRB determination will be made regarding whether a new consent needs to be obtained from participants who provided consent, using a previously approved consent form.

2. PROTOCOL SUMMARY

2.1 SYNOPSIS

Title: Phase 2 Trial of Safety, Immunogenicity, and Efficacy against *Plasmodium falciparum* Malaria of PfSPZ Vaccine in Children in Mali

Study Description: This is a clinical trial of Sanaria® PfSPZ Vaccine, a non-adjuvanted, live (metabolically active), radiation-attenuated, non-replicating, whole sporozoite (SPZ) vaccine designed to prevent malaria infection caused by *Plasmodium falciparum* (Pf).

In this randomized, double-blind, placebo-controlled trial, approximately 268 (up to 290) healthy children aged 6-10 years will be administered three doses of 9.0×10^5 Pf sporozoites (PfSPZ) of PfSPZ Vaccine (or placebo) at 1, 8, and 29-days using direct venous inoculation (DVI).

The study is composed of a single cohort with two arms enrolled concurrently:

Arm 1 (PfSPZ Vaccine): (n = ~134) children ages 6 – 10 will receive three doses of PfSPZ Vaccine (9.0×10^5 PfSPZ) via direct venous inoculation (DVI) at 1, 8, and 29 days

Arm 2 (normal saline): (n = ~134) children ages 6 – 10 will receive normal saline via DVI at 1, 8, and 29 days

All subjects will receive artemether-lumefantrine (AL) approximately 1- 2 weeks before the first and, if there is evidence of significant malaria transmission in the community or the rainy season begins, a third dose of PfSPZ Vaccine or normal saline for clearance of *Pf* parasitemia.

Vaccinated participants and non-immunized placebo controls will be monitored using passive and active case detection for development of *Pf malaria with symptoms* for 26 weeks after V3 through the natural malaria transmission season to estimate vaccine efficacy (VE). Case ascertainment will be prompted by clinical signs and symptoms of acute malaria, with subsequent confirmation of parasitemia by TBS. Participants will be monitored retrospectively for *Pf malaria* (parasitemia) as a secondary endpoint.

Note: for the purposes of this protocol the following definitions apply:

Primary case definition:

Pf malaria with symptoms is defined as a positive thick blood smear at a density of >1000 parasites/uL (P/uL) plus:

- Measured axillary temperature ≥ 37.5 degrees Celsius or history of fever (subjective or objective) in the last 24 hours, or,
- Symptoms of malaria:
 - Verbal individual (individual able and willing to answer questions): A verbal individual is considered symptomatic if reporting at the time of evaluation at least two of the following symptoms/symptom groups: headache, chills and/or rigors, malaise and/or fatigue, dizziness and/or light-headedness, myalgias and/or arthralgias; or
 - Non-verbal individual (small child or any individual unable or unwilling to answer questions): A non-verbal individual is considered symptomatic if manifesting at the time of evaluation at least two of the following signs/sign groups: drowsiness, irritability and/or fussiness, inability and/or refusal to eat or drink, prostration; or
- Any individual: Signs of severe malaria (e.g. impairment of consciousness, severe anemia, hemoglobinuria, acute kidney injury, etc.)

Secondary case definition:

Pf malaria with symptoms is defined as a positive thick blood smear at a density of > 0 P/uL plus:

- Measured axillary temperature ≥ 37.5 degrees Celsius or history of fever (subjective or objective) in the last 24 hours, or,
- Symptoms of malaria as defined in the primary case definition; or
- Meeting criteria for severe malaria

Pf malaria is defined as:

- At least one unambiguous asexual parasite on thick blood smear identified by two independent microscopists after each examining $0.50 \mu\text{L}$ of blood in a study participant

Objectives:

Primary Objectives:

1. To describe the safety of PfSPZ Vaccine in children with respect to the occurrence of possibly, probably, or definitely related serious adverse events (SAEs).
2. To measure VE against first episode of *Pf malaria with symptoms* by time-to-event analysis.

Secondary Objectives:

1. To assess the safety of PfSPZ Vaccine with respect to the occurrence of unsolicited AEs, laboratory abnormalities, solicited AEs.
2. To measure VE against first episode of *Pf malaria (parasitemia)* with or without associated symptoms by time-to-event analysis.
3. To measure antibody responses to *Pf circumsporozoite protein (CSP)* and their association with protection.

Exploratory Objectives:

1. To assess the immune response to PfSPZ Vaccine in children.
2. To assess genetic relatedness of the PfSPZ Vaccine parasite strain to malaria infection parasites.
3. To measure VE using other outcome measures such as against all episodes of *Pf malaria with symptoms* and *Pf malaria* rather than against the first episode, using proportional analysis, or using ITT or ATP populations, or severity of malaria infections or hemoglobin concentration.
4. To explore the relationship between detectable parasitemia prior to vaccination and VE.

Endpoints:

Primary Endpoints:

1. Proportion of vaccinees compared to controls experiencing related SAEs from V1 to 26 weeks after V3
2. VE computed as one minus the estimated hazard ratio (HR) (time-to-event analysis) for first episode of *Pf malaria with symptoms* from 2 weeks after V3 to 26 weeks after V3 in the modified ITT (mITT) population.

Secondary Endpoints:

1. Safety and tolerability in children
 - The differences in proportions of vaccinees compared to controls experiencing unsolicited AEs from the time of V1 to 14 days after V3 (or last immunization).

- The differences in proportions of vaccinees compared to controls experiencing laboratory abnormalities from time of V1 to 14 days after V3.
- The differences in proportions of vaccinees compared to controls experiencing solicited Aes during the 7 days following each immunization.
- 2. VE computed as one minus the estimated hazard ratio (HR) for first episode of *Pf malaria* detected by thick blood smear (TBS), from 2 weeks after V3 to 26 weeks after V3 in the mITT population.
- 3. Antibody levels to PfCSP by standardized ELISA comparing protected and unprotected vaccinees and controls.

Exploratory Endpoints:

- 1. Humoral and cellular immune responses to PfSPZ Vaccine
- 2. Genotyping of peripheral blood Pf parasites
- 3. Additional measures of VE
 - VE against all episodes (rather than first episode) of *Pf malaria with symptoms* and *Pf malaria* by Cox regression analysis
 - VE computed by proportional (binary) analysis (1 – risk ratio) for first episode of *Pf malaria* detected by TBS, from 2 weeks after V3 to 26 weeks after V3 in the intention-to-treat (ITT), mITT and according to protocol (ATP) populations (whole group and subgroups)
 - VE computed as one minus the estimated HR for first episode of *Pf malaria* detected by TBS, from 2 weeks after V3 to 26 weeks after V3 in the ITT and ATP populations (whole group and subgroups)
 - VE for *Pf malaria* measured by and nucleic acid detection in children from 2 weeks after V3 to 26 weeks after V3 using both (time to event, proportional/binary)
 - VE by both time-to-event and proportional/binary analyses for first episodes of *Pf malaria with symptoms* with
 - o parasite density > 500 parasites/ μ L, or
 - o parasite density > 5000 parasites/ μ L
 - or *Pf malaria with symptoms* characterized by:
 - o grade 3 signs or symptoms,
 - o associated with fever and convulsions, or
 - o hospitalization, or
 - o other clinical measures in vaccinees vs. controls
 - Rates of anemia (grade 1, grade 2, grade 3) in vaccinees vs. controls.
- 4. Retrospective malaria qPCR values taken prior to presumptive AL treatment and vaccination

Study Population:	Approximately 268 (maximum 290) healthy children (6 to 10 years of age), resident in Bancoumana and surrounding villages, Mali. Given the potential for dropouts between AL dosing and first vaccinations, up to 290 participants will be dosed with AL prior to first vaccination in order to ensure the target vaccination numbers are met. All participants dosed with AL will also be offered vaccination (or placebo).
Phase:	2
Description of Sites/Facilities	Malaria Research and Training Center (MRTC) research clinic in Bancoumana, Mali
Enrolling Participants:	
Description of Study Intervention:	Radiation attenuated, aseptic, purified, vialled, cryopreserved, NF54 Plasmodium falciparum sporozoites (referred to as PfSPZ Vaccine) produced by Sanaria Inc. will be administered via DVI at dose 9.0×10^5 PfSPZ at 1, 8, and 29 days Normal saline administered via DVI at 1, 8, and 29 days
Study Duration:	22 months March 2022-July 2022 (screening + enrollment + vaccinations) January 2023 (completion of follow-up) January 2024 (completion of data analyses)
Participant Duration:	Approximately 9 months

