C) On days where multiple research assays are collected, if unable to obtain blood for all samples, collection should be prioritized in the following order: 1) Humoral, 2) Transcriptional, 3) Ex-vivo, 4) Cellular. If research blood draws are not fully completed this will not be considered a protocol deviation.
D) For humoral assays, 2-5mls can be collected based on investigators discretion.
E) For cellular assays, 5-10mls can be collected based on investigators discretion.
F) ≤ 15ml of blood should be drawn per day in total; volume amounts per tube are estimates
G) Only hemoglobin measurement is required
H) If clinically indicated
I) Starting after vaccination #1, if the subject has malaria symptoms AND has a positive blood smear (BS) then he/she should return within 48 hours from draw of positive BS for additional sample collection, as needed (ex-vivo, transcriptional assay, qPCR). Subjects/guardians may refuse research blood draws without a protocol deviation. Preference will be to obtain BS positive blood samples for the FIRST positive smear after vaccination #3, >14 days post antimalarial treatment, new positive BS after having a negative BS >28 days.
1) qPCR to be collected at unscheduled malaria positive BS visit if sample not obtained within the last two days with the positive blood smear
2) parasite purification should be collected at unscheduled malaria positive BS visit if not collected in the last 28 days. If collected in the last 28 days, this 4ml collection can be deferred.
3) ex-vivo: to be collected at unscheduled malaria positive BS visit if sample has not been completed in the previous 2 days.
J) Tube types listed in this table may be substituted for acceptable alternatives if the PI and the leads of the immunology and/or clinical labs (as applicable) agree to the change. Any substitutions will be documented in lab logs.

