6.2 EXCLUSION CRITERIA

An individual who meets any of the following criteria will be excluded from participation in this study:

1. Medical, behavioral, cognitive, or psychiatric disease that in the opinion of the investigator affects the ability of the participant's parent and/or legal guardian to understand and comply with the study protocol
2. Menstruating females (in order to avoid cultural implications of further assessing pregnancy potential i.e. sexual activity in this age group)
3. Hemoglobin (Hgb), WBC, absolute neutrophils, and platelets outside the local laboratory-defined limits of normal and \geq Grade 2 (subjects may be included at the investigator's discretion for 'not clinically significant' abnormal values)
4. Alanine transaminase (ALT) or creatinine (Cr) level above the local laboratory-defined upper limit of normal and \geq Grade 2 (subjects may be included at the investigator's discretion for 'not clinically significant' abnormal values)
5. Infected with human immunodeficiency virus (HIV), hepatitis B, or hepatitis C
6. Sickle cell disease by history
7. Taking or planning to take seasonal malaria chemoprophylaxis
8. Clinically significant abnormal electrocardiogram (ECG) such as abnormal QTc
9. History of receipt of the following:
 - Investigational malaria vaccine in the last 2 years
 - Immunoglobulins and/or blood products within 6 months of enrollment
 - Investigational product within 3 months of enrollment
 - Chronic (\geq 14 days) oral or IV corticosteroids (excluding topical or nasal) at immunosuppressive doses (i.e., prednisone \geq 20 mg/day or equivalent) or immunosuppressive drugs within 30 days of enrollment
 - Live vaccine within 30 days of enrollment
 - Killed vaccine within 14 days of enrollment or planned receipt of a killed vaccine within 14 days of scheduled vaccination
10. Known medical problems:
 - Pre-existing autoimmune or antibody-mediated diseases (e.g. systemic lupus erythematosus, rheumatoid arthritis, multiple sclerosis, Sjögren's syndrome, or autoimmune thrombocytopenia)
 - Severe asthma (defined as asthma that is unstable or required emergent care, urgent care, hospitalization, or intubation during the past two years, or that has required the use of oral or parenteral corticosteroids at any time during the past two years)
 - Immunodeficiency disorder
 - Asplenia or functional asplenia
 - Diabetes
 - Deep venous thrombosis or thromboembolic event

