Arthralgia	No interference with activity	Some interference with activity	Significant; prevents daily activity	ER visit or hospitalization
Nausea/ Vomiting	No interference with activity or 1 – 2 episodes/24 hours	Some interference with activity or > 2 episodes/24 hours	Prevents daily activity, requires outpatient IV hydration	ER visit or hospitalization for hypotensive shock
Seizures- includes new or pre-existing febrile seizures	NA	NA	Seizure(s) that are not prolonged or repetitive	Prolonged and repetitive seizures (e.g., status epilepticus) OR Difficult to control (e.g., refractory epilepsy)

Abbreviations: ER, emergency room; IV, intravenous; PO, “per os” or oral administration.

¹ The definitions provided in the table are modified versions taken from the FDA Guidance for Industry “Toxicity Grading Scale for Healthy Adults and Adolescent Volunteers Enrolled in Preventive Vaccine Clinical Trials” dated September 2007 and DAIDS Table for Grading the Severity of Adult and Pediatric Adverse Events version 2.1 July 2017.

Mali Laboratory AE Grading for Pediatric Population

Hematology and Biochemistry Values ^{1, 2}	Mild (Grade 1)	Moderate (Grade 2)	Severe (Grade 3)	Potentially Life Threatening (Grade 4)
Hemoglobin (Male/Female) - gm/dL	7.5 – 8.4	6.1 – 7.4	5.0 – 6.0	< 5.0 g/dL
WBC Increase - 10³/µL	14.5 – 16.0	16.1 – 20.0	20.1 – 30.0	>30.0
WBC Decrease - 10³/µL	2.5 – 3.3	1.5 – 2.4	1.0 – 1.4	< 1.0 with or without fever
Neutrophil/Granulocyte Decrease³ - 10³/µL	0.75 – 0.99	0.50 – 0.74	< 0.50	< 0.50 with fever
Platelets Decreased - 10³/µL	100 – 120	70 – 99	25 – 69	< 25
Creatinine (Male/Female) - µmol/L	95.00 – 119.99	120.00 – 149.99	150.00 – 200.00	> 200.00 and requires dialysis
Liver Function Tests/ALT - U/L	75.0 – 150.9	151.0 – 300.9	301.0 – 600.0	> 600.0

Abbreviations: ALT, alanine transaminase; WBC, white blood cell.

¹ The laboratory values provided in the tables serve as guidelines and are dependent upon institutional normal parameters. Institutional normal reference ranges should be provided to demonstrate that they are appropriate.

² The clinical signs or symptoms associated with laboratory abnormalities might result in characterization of the laboratory abnormalities as Potentially Life Threatening (Grade 4). For example, a low sodium value that falls within a grade 3 parameter should be recorded as a grade 4 hyponatremia event if the subject had a new seizure associated with the low sodium value.

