Appendix B: Institutional Normal Laboratory Values for Children

Hematology Reference Intervals*

	Reference Interval	Units
WBC- Leukocytes	4.8 – 11.2	$10^3/\mu\text{L}$
Hemoglobin	9.1 – 13.3	g/dL
Platelet Count	188 – 551	$10^3/\mu\text{L}$
Absolute Granulocyte Count	1.4 – 5.9	$10^3/\mu\text{L}$

*Based on children ranging in age from 5 to 9 years old (based on sampling done at Bancoumana and Doneguebougou research sites, Mali)

Biochemistry Reference Intervals*

	Reference Interval	Units
ALT	11.5 – 53.0	U/L
Creatinine	< 80.6	$\mu\text{M/L}$

*Based on children ranging in age from 5 to 9 years old (based on sampling done at Bancoumana and Doneguebougou research sites, Mali)

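### The haemoglobin-concentration objective is assessed only through Grade 1–3 anaemia rates and has no analysis in the SAP; a Day 211 concentration comparison would be more sensitive and needs no new samples

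*Protocol*

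**What the plan says.** Protocol 2.1 Synopsis, exploratory objective 3, lists other outcomes on which efficacy is to be measured and ends with "or severity of malaria infections or hemoglobin concentration". Section 4 (Objectives and Endpoints) repeats it. The only corresponding endpoint, in both places, is "Rates of anemia (grade 1, grade 2, grade 3) in vaccinees vs. controls". It names no visit, time window, grading scale or test.

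The protocol's one haemoglobin grading table is in Appendix A: "Hemoglobin (Male/Female) - gm/dL 7.5 – 8.4 6.1 – 7.4 5.0 – 6.0 < 5.0 g/dL", for Grades 1 to 4 in order. Appendix B gives the local reference interval, "Hemoglobin 9.1 – 13.3 g/dL", with the footnote "Based on children ranging in age from 5 to 9 years old" and sampling at Bancoumana and Doneguebougou.

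Haemoglobin is measured at screening and repeated before V1 if that sample is 28 days old or more (2.3 Schedule of Activities, Table 1, footnote L). Table 2 schedules a final blood count with footnote G: "Only hemoglobin measurement is required".

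Protocol section 10 refers the methods for exploratory objectives to the SAP. SAP 3.2 and 3.3 cover symptomatic malaria, parasitaemia, immune responses, the sieve analysis, recurrent episodes and baseline parasitaemia. They do not mention haemoglobin or anaemia.

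**The concern.** The objective is about a continuous quantity. The endpoint counts children below a cut-off that lies 0.7 g/dL under the local lower limit of normal (9.1 − 8.4). A child who falls from 12 to 8.5 g/dL counts as having no anaemia, and values of 8.5–9.0 are below normal but ungraded. Read literally, a child below 5.0 g/dL is not counted either, because Grade 4 is not listed.

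Protocol 3.3.2 names fewer poor outcomes from secondary anaemia as a possible direct benefit for vaccinees. If the only planned measure is insensitive, an absence of difference would be hard to interpret, and any later analysis of the concentration would be post hoc.

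**Working it through.** **Power figures in the plan.** The documents give no power, event rate or SD for haemoglobin. The nearest figure is Table 15 for the primary endpoint: 82% at 120 per arm, control risk 0.35, VE 0.5. It reproduces with Freedman's log-rank formula and 10% drop-out taken from the 120:
- n = 108 per arm; HR = ln(1 − 0.175)/ln(1 − 0.35) = 0.447.
- Events = 108 × (0.35 + 0.175) = 56.7.
- z = √56.7 × (1 − 0.447)/(1 + 0.447) − 1.96 = 0.92, so power is 82.1%.

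I therefore use 120 per arm, with 108 as a check.

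**Is the Day 211 haemoglobin scheduled for everyone?** The stated Day 211 maximum is 13 mL. Blood count 0.5 + smear 0.5 + qPCR 0.5 + humoral 5 + cellular 5 + transcriptional 1 + ex vivo 0.5 = 13. Without the blood count the total is 12.5, so the footnote G sample belongs to that visit.

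**Distribution (assumption).** Read the Appendix B interval as the central 95% of a normal distribution: mean (9.1 + 13.3)/2 = 11.2, SD (13.3 − 9.1)/(2 × 1.96) = 1.07. With values recorded to one decimal, Grade 1 or worse means below 8.45.
- No shift: Φ((8.45 − 11.2)/1.07) = Φ(−2.57) = 0.5%, or 0.6 child per 120.
- Reading the interval as 90% or 99% coverage gives 1.6% or 0.04%.
- Grade 4 stays below 0.05% for mean falls up to 2.0 g/dL under all three readings.

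**Power.** For the mean, power ≈ Φ(d/SE − 1.96) with SE = 1.07 × √(2/120) = 0.138. With baseline correlation 0.5 (assumption), the SD becomes 1.07 × √(1 − 0.25) = 0.93. The graded comparison uses exact power of a two-sided 0.05 Fisher test on any grade.

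| Control fall (g/dL) | Control rate | Rate with 0.5 benefit | Fisher power | Rate with 0.2 benefit | Fisher power |
|---|---|---|---|---|---|
| 0 | 0.5% | 0.1% | <1% | 0.3% | <1% |
| 1.0 | 5.1% | 1.8% | 16% | 3.4% | 5% |
| 1.5 | 12.2% | 5.1% | 40% | 8.8% | 9% |
| 2.0 | 24.2% | 12.2% | 62% | 18.8% | 14% |

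The comparison of means does not depend on the control fall:
- Benefit 0.5 g/dL: 0.5/0.138 − 1.96 = 1.65, power 95% (99% with baseline adjustment).
- Benefit 0.2 g/dL: 0.2/0.138 − 1.96 = −0.51, power 30% (39%).

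At 108 per arm, for a 0.5 g/dL benefit, the graded figures for falls of 1.0–2.0 are 14–57% and the mean gives 93%. If the SD is 1.3 rather than 1.07, the unadjusted mean at 120 per arm has 85% power for 0.5 g/dL and 22% for 0.2.

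**The case against.** A reader might infer that almost no child can qualify as anaemic. The documents do not support that. Appendix B states no coverage, season or health status, and trial children at the end of a malaria season may be lower. Protocol 8.1 (pausing criteria) calls Grade 2 haemoglobin drops common in African children. Table 7 shows any-grade haemoglobin abnormalities in 20.7% of vaccinees and 28.3% of placebo children in Kenya. Table 5 shows one Grade 2 decrease among six placebo children aged 6–10 in Tanzania. None of these states that the Appendix A scale was used. Table 9 points the other way, with no haemoglobin decrease of Grade 2 or higher in 200 Gabonese children, on a scale also not given. The rate is simply unknown.

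A reader might also take the 95% as what the concentration analysis will achieve. It belongs to an assumed 0.5 g/dL benefit. At control risk 0.35 and VE 0.5, 17.5 percentage points fewer vaccinees have an episode. If each prevented case saves 1.0 g/dL at Day 211 (assumption), the mean difference is 0.175 g/dL and power is about 24%, or 31% with baseline adjustment. Cases are treated promptly and follow-up ends in January, after the July–December wet season, so a small difference is plausible. This stands.

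Nor does omitting Grade 4 explain the low power: it is too rare to matter there, and severe anaemia with more than 1000 parasites/µL already meets the primary case definition. The omission is a gap in definition. Finally, graded anaemia is clinically readable, no Fisher test is specified for this endpoint, and the objective is exploratory and unpowered. All of that is right. It does not give the concentration objective an analysis.

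**Conclusion.** The mismatch between objective and endpoint, and the SAP's silence on haemoglobin, are established from the text. Use of Appendix A is inferred, because it is the protocol's only haemoglobin grading table. Grades were less sensitive than the mean in every scenario tested, so that conclusion does not require anaemia to be rare. The size of the gap does depend on assumptions: a normal distribution from Appendix B, an SD of 1.07, a uniform shift in the mean, and a Fisher test as a stand-in for an unspecified comparison. It is also not established that the trial would report a null caused by the cut-off, since the true anaemia rate and the true effect are both unknown. This is a low-priority improvement to one exploratory measure. The primary and secondary results are unaffected.

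**What to change.** Add one paragraph to the SAP as an exploratory efficacy analysis: Day 211 haemoglobin concentration compared between arms by ANCOVA, adjusted for the last haemoglobin before V1, reporting the mean difference with a 95% CI.

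Keep graded anaemia as a descriptive table. State the visit or window and the grading scale, show Grade 1 or worse with Grade 4 included, and add the proportion below 9.1 g/dL.

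The cost is that paragraph and one extra model. No new samples or visits are needed. The change should be made before unblinding, including the preliminary unblinded analysis in Protocol 10.4.5.
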